4.4 Safety Objectives

To evaluate the safety and tolerability of AK002 by determining incidence and severity of adverse events, study withdrawals due to adverse events, changes in vital signs and laboratory tests including immunogenicity, changes in concomitant medication use due to adverse events, and other safety parameters.

4.5 Target of Estimation

The estimand (target of estimation) for Protocol AK002-016 is:

In patients with EG and/or EoD, what is between group (AK002 vs. Placebo) difference in the proportion of tissue eosinophil responders at Week 24, and group difference in TSS from baseline to Weeks 23–24 as measured by the patient-reported outcome (PRO) questionnaire.

The sections below describe the attributes of the estimand consistent with the ICH E9 Addendum (FDA, 2021).

4.5.1 Population Targeted by the Scientific Question

The population targeted by the scientific question is defined by the inclusion and exclusion criteria as part of the study protocol. Patients must have a histological diagnosis of EG and/or EoD.

A key aspect of eligibility is that subjects must complete at least 4 daily PRO questionnaires per week for a minimum of 3 weeks during the screening period. In addition, subjects must have a weekly average score of abdominal pain, nausea, or diarrhea ≥ 3 on the PRO questionnaire (score from 0–10) for at least 2 weeks of screening and a weekly average TSS of ≥ 10 for at least 2 weeks of screening.

4.5.2 Variables of Interest (or Endpoint) Required to Address the Scientific Question

The co-primary endpoints to be obtained for each subject in this study to address the scientific question are Tissue Eosinophil Responders at Week 24 and change in TSS from Baseline to Weeks 23–24 as measured by the PRO questionnaire.

4.5.3 Treatment

AK002 or placebo administered to subjects on Days 1, 29, 57, 85, 113, and 141.

4.5.4 Intercurrent Events

The events below are considered Intercurrent events (ICE) confounding with the efficacy outcomes.

- Premature discontinuation from the study.
- Use of prohibited/restricted medication.

Intercurrent events are described above, and further clarification and handling of ICE including prohibited/restricted medications are detailed in the Statistical Analysis Plan (SAP).

4.5.5 Strategy for Handling Intercurrent Events

If a prohibited/restricted medication is started during the course of the study, the patient may be withdrawn from study treatment and followed for the 12-week follow-up period. In addition, the follow-up EGD may not be performed. Thus, for the analysis of the study product estimand, tissue eosinophil values and TSS scores will be counted as non-responders for binary variables and set to missing for continuous outcomes from the point when an ICE occurs. An appropriate method for handling missing data through statistical modeling (e.g., multiple imputation [MI]) will be used (as detailed in the SAP). The estimand will provide an answer to the question that is crucial to individual subjects:

If I take this study medication as part of my treatment regimen, without adding any further medications that may impact the underlying disease or exit the study prematurely, what improvements in histology and PRO symptoms might be anticipated after 24 weeks?

4.5.6 Summary Measures

- Percent (and 95% confidence interval [CI]) of subjects having tissue eosinophil response at Week 24 in the AK002 and placebo treatment groups and the absolute difference (and 95% CI) in the percent response between treatments.
- Least squares mean (LSM) (and standard error [SE]) of change from baseline to the average of Weeks 23–24 TSS and the between treatment difference in the AK002 and placebo treatment groups LSM.

5. Study Design

5.1 Study Overview

This is a Phase 3, multicenter, randomized, double-blind, placebo-controlled study to evaluate the efficacy and safety of AK002 in patients with EG and/or EoD who have an inadequate response with, lost response to, or were intolerant to standard therapies.

Patients enrolled in the study will receive 6 infusions of placebo or AK002 administered every 4 weeks and will be followed for 12 weeks after the last dose unless patients elect to enter the optional long-term extension study.

Patients will be consented and then screened for 3–5 weeks (18–45 days) prior to Day 1. Patients who meet all eligibility criteria can be enrolled into the study. Patients who do not meet all eligibility criteria at screening or who qualify at screening but are not enrolled may be assigned a new patient identification number and rescreened once. Patients rescreened within 30 days of signing the initial consent will not need to sign a new informed consent form (ICF) providing no changes have been made to the ICF.

The study is designed as follows:

- An 18 to 45-day screening period with baseline evaluations for study eligibility including active symptoms of disease (gathered by the patient reported outcome [PRO] questionnaire completed during screening) and EGD with biopsy.
- Prior EGD may be used for eligibility as long as the EGD occurred within 30 days of the first screening visit for the AK002-016 study and were performed and centrally assessed as

for the AK002-016 study.

- If patients meet histology and symptom eligibility criteria, they will be randomized and stratified by the highest weekly TSS of disease activity recorded during the screening period (<28 or \geq 28 strata) and whether the patient is EoD-only. The IRT will assign patients 1:1 to receive AK002 or placebo; 6 doses will be received.
- Pre-study medications and dietary restrictions should remain unchanged throughout the screening period and throughout the study. Systemic or swallowed steroids above 10 mg daily prednisone (or the equivalent thereof) will not be allowed except as an approved premedication prior to infusion, to treat an IRR that occurs during infusion, or the use is due to unforeseen circumstances when it is deemed medically necessary to treat an unrelated medical condition.
- Eligible patients will receive the first dose of placebo or AK002 (1 mg/kg) on Day 1, with premedication of 60 mg oral prednisone 12–24 hours prior to the start of the infusion.
- If the study drug is well tolerated (no stopping rules being met), patients will receive 5 additional doses of placebo or AK002 (3 mg/kg) on Days 29, 57, 85, 113, and 141. With the exception of Day 1, steroid premedication will only be allowed with the written approval of the Medical Monitor.
- Patients will remain at the site for at least 1 hour of observation following the end of the infusion.
- During the Treatment period patients will return to the clinic for study visits as described in the Schedule of Events ([Table 1](#)).
- Daily administration of the PRO questionnaire (including any appropriate additional questions) throughout the study and the follow-up period for all patients.
- An EGD with biopsy will be performed on Day 169 (\pm 3) or 28 (\pm 3) days after last dose of study drug if patient terminates early.
- Follow-up will occur for 84 (\pm 3) days after the last dose of study drug unless patients decide to enter the long-term extension study. Follow-up visits for patients opting not to enter the extension study will occur on Day 176 (\pm 3), Day 197 (\pm 3) and Day 225 (\pm 3).
- Patients who satisfactorily complete AK002-016 have the option to receive AK002 in a separate open-label extension study if all eligibility criteria for the extension study are satisfied. Patients who enroll in the AK002-016X extension study may begin the extension study dosing 1 day after completing the Day 176 visit of this protocol.

- Total study duration is approximately 35–37 weeks. For patients entering the AK002-016X extension study, the total study duration may be as short as 28 weeks.
- Patients may enroll in the AK002-016X extension study any time after the Day 176 visit in the main study has occurred. The Day 197 and Day 225 main study visits will occur if the patient does not enroll in the extension study prior to the scheduled date of these visits. A patient enrolling in the AK002-016X study prior to Day 197 will not complete the Day 197 or Day 225 procedures under this protocol. Open-label dosing and follow-up will occur under the AK002-016X extension study.

5.2 Schedule of Events

The overall schedule of procedures and assessments are depicted in [Table 1](#).

Table 1 Schedule of Assessments

	Screening (18–45 days)		Treatment Period (20 weeks)								Follow-Up Period ³⁰ (12 weeks)			
	Baseline ¹	Prior to Day 1	Dose 1 Day 1	Day 8 (±2 days)	Day 15 (±2 days)	Dose 2 Day 29 (±3 days)	Dose 3 Day 57 (±3 days)	Dose 4 Day 85 (±3 days)	Dose 5 Day 113 (±3 days)	Dose 6 Day 141 (±3 days)	Day 169 (±3 days) or 28 days after last dose	Day 176 (±3 days) or 35 days after last dose if ET ²⁹	Day 197 (±3 days) or 56 days after last dose if ET ²⁹	Day 225 (±3 days) or 84 days after last dose if ET ²⁹
Informed consent	X													
Demographics	X		X											
Medical History	X		X											
Prior/Concomitant Medications	X		X			X	X	X	X	X	X	X	X	X
Body weight and height ²	X		X			X	X	X	X	X		X	X	X
Vital Signs ³	X		X			X	X	X	X	X		X	X	X
10 or 12-lead ECG ⁴	X													
Complete Physical Exam ⁵	X													
Symptom-Directed Physical Exam ⁶			X			X	X	X	X	X		X	X	X
Baseline Diet Assessment ⁷	X													
Baseline Diet Compliance ⁸			X			X	X	X	X	X		X	X	X
Stool for Ova and Parasite ⁹	X													
ePRO Activation and Training ¹⁰	X													
ePRO Questionnaire (may include Additional Questions) ¹¹	<-----Complete electronically one time daily----->													
██████████ CCI ██████████	X		X			X	X	X	X	X		X	X	
CCI ██████████	<-----Complete electronically on Screening Day 19, Study Day 7, and Study Day 28----->													
CCI ██████████	<-----Complete electronically on Study Day 7 and Study Day 28----->													
EGD with Biopsy ^{12,14}	X										X			
Blood for Screening Chemistry (includes hCG and FSH) ^{12,15}	X													

Table 1 Schedule of Assessments cont.

	Screening (18–45 days)		Treatment Period (20 weeks)									Follow-Up Period ³⁰ (12 weeks)			
	Baseline¹	Prior to Day 1	Dose 1 Day 1	Day 8 (±2 days)	Day 15 (±2 days)	Dose 2 Day 29 (±3 days)	Dose 3 Day 57 (±3 days)	Dose 4 Day 85 (±3 days)	Dose 5 Day 113 (±3 days)	Dose 6 Day 141 (±3 days)	Day 169 (±3 days) or 28 days after last dose	Day 176 (±3 days) or 35 days after last dose if ET²⁹	Day 197 (±3 days) or 56 days after last dose if ET²⁹	Day 225 (±3 days) or 84 days after last dose if ET²⁹	
Blood for Serology and Strongyloides stercoralis ^{12,16}	X														
Blood for Total Serum IgE ^{12,17}	X											X			
Previous Treatments Review	X														
Eligibility Assessment	X	X	X												
Access IRT: Stratification and Randomization ¹⁸			X												
Access IRT: IP Kit Assignment			X			X	X	X	X	X					
Premedication: Prednisone ¹⁹		X													
Study Drug Administration ²⁰			X			X	X	X	X	X					
Blood for CBC with differential ^{12,21}	X		X	X	X	X	X	X	X	X	X	X	X	X	
Blood for Chemistry ^{12,22}			X	X	X	X	X	X	X	X	X	X	X	X	
Blood for PK ^{12,23}	X			X	X	X	X	X	X	X	X	X	X	X	
Blood for ADA ^{12,24}	X			X	X	X	X	X	X	X	X	X	X	X	
Urine for Urinalysis ^{12,25}	X		X			X	X	X	X	X		X	X		
Dipstick Pregnancy Test ²⁶			X			X	X	X	X	X		X	X		
Non-serious Adverse Events ²⁷			X			X	X	X	X	X	X	X	X	X	
Serious Adverse Events ²⁸			X			X	X	X	X	X	X	X	X	X	
Begin AK002-016X extension study at least 1 day after Day 176 Visit (if applicable) ³¹												X ³³	X ³³	X ³³	
Blood for histamine/tryptase ³²			X			X	X	X	X	X					

Table 1 Notes

ADA: Anti-AK002 antibody
CBC: Complete blood count
ECG: Electrocardiogram
ePRO: electronic Patient Reported Outcome

ET: Early Termination
FSH: Follicle-stimulating hormone
hCG: Human Chorionic Gonadotropin
IP: Investigational Product

IRT: Interactive Response Technology
CCI [REDACTED]
CCI [REDACTED]
PK: Pharmacokinetics

- 1) Baseline screening visit can occur over several days within the screening period. Day 1 can begin as soon as eligibility criteria are met and at least 4 diary entries have been completed during the third week of screening.
- 2) At screening, height (in cm) and weight (in kg) will be recorded. Body weight will also be measured on Days 1, 29, 57, 85, 113, 141 and on follow-up Day 176, Day 197 and Day 225 or 28, 56, and 84 days after last dose, if ET. Current body weight or body weight from 1 day prior will be used to calculate the amount of AK002/placebo to be mixed with NaCl for the appropriate dose to be administered on each infusion day.
- 3) Vital signs will be measured at screening, Days 176, 197, and 225 or 28, 56, and 84 days after last dose if ET and on all dosing days: within 30 minutes predose, 15 minutes (± 5 minutes) after the start of study drug infusion, within 15 minutes following the end of infusion and just prior to discharge. Additional vital signs measurements may be collected at the Investigator's discretion if an IRR occurs. Vital signs including systolic and diastolic blood pressure, pulse, body temperature, and respiratory rate will be measured after the patient has been at rest for ≥ 5 minutes and before any blood draws have been obtained (unless collected for an IRR).
- 4) A 10-lead or 12-lead ECG will be obtained at screening before any blood is drawn and after the patient has been in the appropriate position for ≥ 5 minutes.
- 5) A complete physical examination will be performed by either the Investigator or designee and include the following body system or organ assessments: skin; head, eyes, ears, nose and throat; thyroid; lungs; cardiovascular; abdomen; extremities; lymph nodes; and a brief neurological examination.
- 6) A symptom-directed PE (including assessment of possible infusion site reactions) will be performed by the Investigator or designee, as needed if any symptoms are reported.
- 7) A baseline diet assessment ([Appendix 3](#)) will be performed using standardized questions. Eating patterns, food avoidance behaviors, and confirmed allergies will be captured.
- 8) A baseline diet compliance check will be performed at every study visit, except as noted above, and any variances from the baseline diet documented. Patients should maintain the baseline diet throughout the study.
- 9) Fecal collection kits for Ova and Parasite test will be provided to patients at screening. Collection kits should be returned to the clinical site within 1 day of collection. Negative results must be available prior to randomization.
- 10) Activate PRO questionnaire and provide patient with unique username and password. PRO questionnaire should be activated for all patients on screening Day 1. Patients with concomitant history of asthma or atopic dermatitis will receive an extra question, about each, as appropriate. All patients will receive dysphagia question during screening and will continue to receive the question after enrollment if weekly average dysphagia is ≥ 3 during any 2 weeks of screening.
- 11) PRO should be completed around the same time each day. Prior to enrollment, the PRO weekly averages of abdominal pain, nausea, and diarrhea over the screening period will be calculated and used to assess eligibility. Weekly average Total Symptom Score (TSS6) will be calculated for eligibility and stratification. PRO weekly average for dysphagia will also be assessed prior to enrollment to determine if the patient should continue receiving the 1-question daily dysphagia question.
- 12) Specimen processed by central laboratory. See central laboratory manual for collection and processing details.

Table 1 Notes cont.

- 13) To be completed electronically by patient, in clinic, prior to any blood draw, physical exam, or vital sign measurements.
- 14) See [Appendix 5](#) for biopsy assessments. The post-treatment endoscopy (EGD) and biopsy assessments will be performed on Day 169 (± 3) or 28 (± 3) days after last dose of study drug if ET. If the Day 141 infusion occurs out of window, the EGD should occur 28 (± 3) days from the date of Day 141. Post-treatment EGD biopsy results will be blinded to the site.
- 15) Blood for baseline Chemistry, including hCG and FSH, will be collected during the screening period. Only patients of childbearing potential and post-menopausal women are required to have hCG and FSH testing completed.
- 16) Blood for Serology testing will be collected during screening and will include HBsAg, hepatitis C antibody, anti-HBc, and HIV, as well as *Strongyloides stercoralis*.
- 17) Blood samples for Total Serum IgE will be collected during screening and on Day 176 or 35 (± 3) days after last dose of study drug, if ET.
- 18) Stratification based on TSS of <28 or ≥ 28 and whether patient is EoD-only will occur. Randomization and stratification will be conducted through the IRT system.
- 19) Premedication with 60 mg oral prednisone or approved alternative is required 12–24 hours prior to first infusion. Premedication may be administered prior to subsequent infusions at the Investigator's discretion, but only with written Medical Monitor approval.
- 20) Study drug will be administered as a single peripheral IV infusion over at least 4 hours for Dose 1 and at least 3 hours for Dose 2. Doses 3–6 should occur over at least 2 hours, depending on prior infusion tolerability. Please refer to the Pharmacy Manual.
- 21) Blood for CBC with differential, including absolute blood eosinophil count, will be obtained just prior to each infusion, 1 hour (± 15 minutes) after the end of each infusion as well as during the screening period, and on Days (± 3) 8, 15, 169, 176, 197, and 225 or 35, 56, and 84 (± 3) days after last dose if ET. All differential blood counts from Day 1 (post-dose) through the end of the patient's participation will be blinded to the Sponsor and the site. An unscheduled CBC may be collected at the request of the Safety Monitor.
- 22) Blood for chemistry will be obtained predose on dosing Days 1, 29, 57, 85, 113, and 141, as well as on Days 8, 15, 169, 176, 197, and 225 or 28 (± 3), 35 (± 3), 56 (± 3), and 84 (± 3) days after last dose of study drug if ET.
- 23) Blood for PK will be obtained predose on dosing Days 29, 57, 85, 113, and 141, as well as during screening and on Days 8, 15, 169, 176, 197, and 225 or 28 (± 3), 35 (± 3), 56 (± 3), and 84 (± 3) days after last dose of study drug if ET.
- 24) Blood for ADA will be collected predose on dosing Days 29, 57, 85, 113, and 141, as well as during screening and on Days 8, 15, 169, 176, 197, and 225 or 28 (± 3), 35 (± 3), 56 (± 3), and 84 (± 3) days after last dose of study drug if ET. ADA sample will also be collected any time an immunogenicity-related AE occurs.
- 25) Urine for standard urinalysis will be obtained predose on dosing Days 1, 29, 57, 85, 113, and 141 as well as during the screening period and on Day 176 and Day 197 or 35 (± 3) days and 56 (± 3) days after last dose of study drug if ET.
- 26) A small amount of urine collected for urinalysis will be used for dipstick pregnancy test on all infusion days and on Day 176 and 197 or 35 and 56 (± 3) days after last dose of study drug, for all patients of childbearing potential. Test kits will be supplied by the central laboratory. Tests will be completed on site and evaluated prior to each infusion.
- 27) The capture of non-serious AE and adverse events of special interest will begin after the first dose of study drug has occurred.

Table 1 Notes cont.

- 28) The reporting of SAE occurring after signing Informed consent and prior to the first infusion will be limited to those that relate to screening procedures. The capture of all SAE and AE that are not related to screening procedures will begin at the time of first infusion of study drug.
- 29) Patients who sign the informed consent for the AK002-016X extension study will complete the procedures for Day 176 and may begin open-label dosing in the extension study, if eligible, one day after the completion of Day 176 visit. In this case, patients will not complete the Day 197 or Day 225 procedures under Protocol AK002-016. Open-label dosing and follow-up will occur under the AK002-016X extension study. Patients who choose to enter the AK002-016X extension study after Day 197 but before Day 225 will not complete Day 225 procedures.
- 30) The ET visits should be conducted 28 (± 3), 35 (± 3), 56 (± 3), and 84 (± 3) days after the last dose of study drug or prior to this, if necessary, to ensure compliance with the visit. If only 1 ET visit is possible, EGD and end-of-study blood work may occur on the same day (28 days after last dose and 35 days after last dose visit procedures). If the end-of-study visit occurs more than 35 days after the last dose of study drug, then perform the visit as soon as possible. The procedures listed under the 28-day and 35-day post-study drug visit will be conducted unless otherwise directed by the Medical Monitor.
- 31) The final hematology assessment for AK002-016 **must** be collected **prior to** the subject taking prednisone premedication for AK002-016X. Therefore, dosing in AK002-016X must take place at least 1 day after completion of the Day 176 visit for AK002-016. Subjects may start AK002-016X dosing 1 day after completion of the Day 176 Visit.
- 32) Blood samples for histamine and tryptase to be collected within 1–2 hours of start of symptoms if there is any suspicion of anaphylaxis.
- 33) For patients who do not start the extension study before Day 197 or Day 225, visit procedures will occur according to the AK002-016 study.

6. Criteria for Evaluation

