Subsequent infusions in multiple dose cohorts were associated with fewer IRR when compared with the first infusion. Therefore, the proposed dosing regimen is a starting dose of 1 mg/kg, with a second dose of 3 mg/kg, followed by 4 doses of 3 mg/kg for subsequent infusions for this Phase 3 study with AK002 in patients with EG and/or EoD.

4. Study Objectives

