11.3.5 Symptom-Directed Physical Examination

A symptom-directed physical exam, an examination of reported or observed subject symptoms warranting examination (in the opinion of the Investigator), including assessments of possible infusion site reactions and IRR, will be performed by either the Investigator or a qualified designee at all study visits during the treatment period and follow-up period. New, abnormal physical exam findings must be documented and will be followed by the Investigator or Subinvestigator at the next scheduled visit or sooner if clinically indicated or referred to a non-study Physician.

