- c) Observe the patient for at least 1 hour after the end of infusion. Collect vital signs just prior to discharge.

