12.7 Day 28 (not a Clinic Visit)

- 1) **CCI** [REDACTED] ([Appendix 8](#))
- 2) **CCI** [REDACTED] ([Appendix 9](#))

12.8 Day 29 (± 3) – Infusion 2

- 1) Prior to the infusion:
 - a) Assess the patient for AE and SAE.
 - b) Document any changes to concomitant medications.
 - c) Assess baseline diet compliance.
 - d) Assess daily diary compliance (including any additional questions).
 - e) **CCI** [REDACTED]
 - f) Determine body weight.
 - g) Urinalysis
 - h) Perform urine pregnancy test (if patient is of childbearing potential).
 - i) Collect vital signs within 30 minutes of the start of the infusion.
 - j) Perform symptom-directed physical exam, as needed.
 - k) CBC with differential
 - l) Chemistry
 - m) Blood for PK
 - n) Blood for ADA
 - o) The IRT will be accessed, and the patient's PID and body weight will be entered.
- 2) The study pharmacist will prepare study drug using the current body weight obtained and the dosage (3 mg/kg) and kit number(s) provided by the IRT.
- 3) Infusion of Study Drug:
 - a) Infuse 100 mL of study drug over at least 3 hours using an infusion pump. See the Pharmacy Manual for infusion rates. Record the start and stop times of the infusion including any times the infusion is interrupted.
 - b) Collect vital signs 15 (± 5) minutes after the start of infusion.
 - c) If anaphylaxis is suspected, a sample of blood should be obtained for plasma histamine level and tryptase within 1–2 hours of the onset of the symptoms. Also, an unscheduled ADA blood sample may be obtained if an immunogenicity-related AE is suspected.
- 4) Post-infusion:
 - a) Collect vital signs within 15 minutes of the end of the infusion.
 - b) Collect CBC with differential 1 hour (± 15 minutes) after the end of the infusion.

- c) Observe the patient for at least 1 hour after the end of the infusion. Collect vital signs just prior to discharge.

12.9 Day 57 (± 3) – Infusion 3

- 1) Prior to the infusion:
 - a) Assess the patient for AE and SAE.
 - b) Document any changes to concomitant medications.
 - c) Assess baseline diet compliance.
 - d) Assess daily diary compliance (including any additional questions).
 - e) **CCI** [REDACTED]
 - f) Determine body weight.
 - g) Perform urine pregnancy test (if patient is of childbearing potential).
 - h) Collect vital signs within 30 minutes of the start of the infusion.
 - i) Perform symptom-directed physical exam, as needed.
 - j) CBC with differential
 - k) Chemistry
 - l) Urinalysis
 - m) Blood for PK

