13.4 Infusion-Related Reactions

All AE considered by the Investigator *to be related to the infusion* of the biological substance and occurring within 24 hours of the start of the study drug infusion should be captured as 1 AE, termed “IRR.” Common symptoms of IRR include but are not limited to:

- Flushing
- Chills
- Back or abdominal pain
- Chest discomfort or tightness
- Dizziness
- Shortness of breath
- Headache
- Hypotension or hypertension
- Nausea
- Vomiting
- Sweating
- Fever
- Urticaria
- Pruritus
- Bronchospasm

All symptoms experienced by a patient during an IRR will be listed in the eCRF under 1 IRR, unless the Investigator believes a symptom is not part of the IRR, in which case it will be recorded separately. The start time of the IRR will be captured as the start time of the first symptom and the end time of the IRR will be captured as the end time of the last symptom.

Any medications used within 24 hours of an infusion for the treatment of an IRR are not considered prohibited medications.

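### No AE, SAE or medication inquiry is scheduled at the Day 8 and Day 15 visits, so events after Day 1 discharge are first actively sought at Day 29

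*Protocol*

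**What the plan says.** Protocol Section 5.2, Table 1, marks "Non-serious Adverse Events" and the serious AE row at Day 1, Day 29 and every later visit. The row "Prior/Concomitant Medications" is marked at baseline, Day 1, Day 29 and every later visit. All three are blank at Day 8 and Day 15. The SAP repeats the table in Section 3.1 with the same blanks.

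Sections 12.5 (Day 8) and 12.6 (Day 15) each list CBC with differential, chemistry, ADA and PK, and nothing else. The first later instruction to "Assess the patient for AE and SAE" is in Section 12.8, before the Day 29 infusion.

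For Day 1, Table 1 note 27 says: "The capture of non-serious AE and adverse events of special interest will begin after the first dose of study drug has occurred". Section 12.3 asks before the infusion only about SAEs related to screening. After it, the list has vital signs, a CBC and the step "Observe the patient for at least 1 hour after the end of infusion", with no AE question.

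Two general sections read differently from the table. Section 11.3.1 has medication changes documented at study visits, with no exception for Day 8 or Day 15. Section 11.3.5 says the symptom-directed examination, which covers IRR, "will be performed by either the Investigator or a qualified designee at all study visits during the treatment period and follow-up period".

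**The concern.** The first four weeks of exposure are where the documents give most reason to ask. Section 2.3 names IRR as the most common treatment-emergent event, and Section 3 reports: "Subsequent infusions in multiple dose cohorts were associated with fewer IRR when compared with the first infusion". Section 13.3 makes IRR and hypersensitivity an AE of special interest.

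Section 13.4 classifies an event as an IRR if the Investigator considers it related to the infusion and it is one "occurring within 24 hours of the start of the study drug infusion should be captured as 1 AE". It also requires start and end times. Classification therefore depends on an onset time known to the hour, which is hard to recover weeks later. For a patient who goes home soon after the infusion, most of the window passes at home.

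The patient is then seen twice, with nothing in the schedule prompting staff to ask what happened. Safety is part of the primary objective (Section 4.1), and the SAP's AE tables can only count what was ascertained. The scheduled inquiry that ends the gap takes place on the day the second, higher dose is due.

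**Working it through.** The plan states no figure on this point. The check is a reading of the schedule plus day and hour arithmetic.

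**Column positions.** Because Table 1 was extracted from PDF, the CBC row serves as a position check. It is marked at baseline, Day 1, Day 8, Day 15, Day 29 and every later visit. Read against the same columns:
- AE and SAE rows: Days 1, 29, 57, 85, 113, 141, 169, 176, 197 and 225.
- Concomitant medication row: baseline and the same ten days.

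Day 8 and Day 15 are the only post-dose visit columns without these marks. Even Day 169, the endoscopy visit, has them, and Section 12.13 lists the collection.

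**Are these clinic visits?** Section 5.1 has patients return to the clinic as set out in Table 1. Only Day 7 and Day 28 are headed as not being clinic visits (Sections 12.4 and 12.7). Day 8 and Day 15 are not.

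**Time from infusion 1 to each contact** (visit day minus Day 1, using the visit windows):
- Day 8 (±2): 6 − 1 = 5 to 10 − 1 = 9 days; nominal 7.
- Day 15 (±2): 13 − 1 = 12 to 17 − 1 = 16 days; nominal 14.
- Day 29 (±3): 26 − 1 = 25 to 32 − 1 = 31 days; nominal 28.

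**Part of the IRR window after discharge.** The window is 24 h from infusion start (Section 13.4). The infusion lasts at least 4 h and observation at least 1 h (Section 12.3).
- Shortest stay: 4 + 1 = 5 h, leaving 24 − 5 = 19 h.
- Infusion extended to the 8 h limit in Section 9.6, with the same 1 h observation: 24 − 8 − 1 = 15 h.

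So 19 h is an upper bound, and longer observation lowers it.

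**Effect of the change.** With inquiry at Day 8 and Day 15, the first question after discharge moves from 25–31 days to 5–9 days. The nominal gap from the last inquiry to dose 2 becomes 29 − 15 = 14 days.

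**Day 1 text against Day 1 mark.** Note 27 makes the non-serious AE mark a post-dose one, yet Section 12.3 has no post-infusion AE step. The table supports capture on site; the visit list does not carry it out.

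**The case against.** The strongest reply is that the gap is partly covered elsewhere. Section 13.1 records all AEs from the first dose, including those volunteered or found on examination or laboratory testing. Section 11.3.1 has medication changes documented at study visits, and Section 11.3.5 puts the symptom-directed examination at all treatment-period visits. This largely stands: the documents do not show that nobody asks. But Section 13.1 governs recording once an event is known and schedules no question. The examination in Section 11.3.5 responds to symptoms already reported or observed. Staff working from Table 1 or from Sections 12.5 and 12.6 would find no prompt, and practice could differ by site.

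The daily PRO does not fill the gap. It covers gastrointestinal symptoms, with single questions on dysphagia, asthma or atopic dermatitis where applicable, and is not an AE inquiry.

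The first-infusion excess also comes from earlier studies. Here only the first infusion has mandatory prednisone premedication (60 mg). Section 2.3 reports no IRR at the first extension-study infusion with 80 mg, though that regimen was used in 20 of 58 patients, after a trial in which two of three arms received AK002. This trial excludes prior exposure. Section 3 also reports very few AEs beyond an infusion window that it does not define. These points lower the expected number of missed events but do not explain the blank cells.

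Infusions 2 to 6 are also followed by about 28 days without scheduled inquiry. By the same arithmetic, up to 24 − 3 − 1 = 20 h (infusion 2) or 24 − 2 − 1 = 21 h (infusions 3 to 6) of their IRR windows fall after discharge. That is correct. What sets infusion 1 apart is that patients already attend twice in the interval.

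Finally, asking at Day 8 still relies on 5 to 9 days of recall. The change shortens recall but does not remove it.

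**Conclusion.** The point holds as a gap in scheduled safety ascertainment and an inconsistency between the schedule and the procedural text. Followed as written, the schedule leaves events after Day 1 discharge first actively sought 25 to 31 days after infusion 1, including up to 19 of the 24 hours of the IRR window. This rests on the minimum infusion and observation times and on Day 8 and Day 15 being attended in clinic.

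A reader might infer more, and the documents do not support it:
- That all first-infusion reactions wait for four-week recall. Day 1 is marked for AE capture after dosing, and reactions during the infusion and observation occur in front of staff.
- That abnormal Day 8 or Day 15 chemistry goes unrecorded unless the patient is asked. Section 11.4 has the Investigator judge every out-of-range value and record clinically significant ones as AEs.
- That events are known to be lost or misclassified. No passage shows this; the risk is inferred from the schedule.
- That efficacy conclusions are affected. The schedule is the same in both blinded arms, and safety parameters carry no formal inference (Section 15).

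The change is worth making because ascertainment improves at visits that already take place.

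**What to change.** 1. In Table 1 of the protocol and its copy in SAP Section 3.1, mark the non-serious AE, SAE, concomitant medication and symptom-directed examination (as needed) rows at Day 8 and Day 15.
2. Add the matching steps to Sections 12.5 and 12.6, so that they agree with Sections 11.3.1 and 11.3.5.
3. At Day 8, add an eCRF prompt for the onset date and time of any event within 24 h of the start of infusion 1.
4. Add a post-infusion AE step to Section 12.3, to match the Day 1 mark and note 27.

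If the sponsor meant Day 8 and Day 15 to be blood draws only, the protocol should say so, give the reason, and limit Sections 11.3.1 and 11.3.5 accordingly.

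The cost is a few minutes at each of two existing visits and the added eCRF prompts. No visit, procedure or staff is added.
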